5.1 Overall Design

This is a phase 1 study designed to evaluate safety, reactogenicity, immunogenicity, and transmission-blocking activity (via SMFA) of Pfs25M-EPA and Pfs230D1M-EPA conjugates formulated on AS01 and transmission-blocking activity (via DSF) of Pfs230D1M-EPA conjugates formulated on AS01 at full and fractional dosing. We will enroll a total of 305 vaccinated subjects to be divided between multiple sites in Mali as shown in [Appendix A](#) and described below.

In Bamako/Sotuba, Mali (N=65)

Dose-escalating, open label, randomized, pilot study

1. Group 1: Pfs25M-EPA/AS01 (n=15)

- **Arm 1a** (n=5), to receive 16 µg Pfs25M-EPA/AS01 on D0, D28, D168
- **Arm 1b** (n=10), to receive 47 µg Pfs25M-EPA/AS01 on D0, D28, D168

2. Group 2: Pfs230D1M-EPA/AS01 (n=15)

- **Arm 2a** (n=5), to receive 13 µg Pfs230D1M-EPA/AS01 on D0, D28, D168
- **Arm 2b** (n=10), to receive 40 µg Pfs230D1M-EPA/AS01 on D0, D28, D168

3. Group 3: Pfs25M-EPA/AS01 and Pfs230D1M-EPA/AS01 (n=15)

- **Arm 3a** (n=5), to receive 16 µg Pfs25M-EPA/AS01 and 13 µg Pfs230D1M-EPA/AS01 on D0, D28, D168
- **Arm 3b** (n=10), to receive 47 µg Pfs25M-EPA/AS01 and 40 µg Pfs230D1M-EPA/AS01 on D0, D28, D168

4. Group 4: Comparator (n=20)

- **Arm 4a** (n=10), to receive ENGERIX-B on D0, D28, and D168
- **Arm 4b** (n=10), to receive ENGERIX-B on D0, D28, and D168

In Bancoumana and Doneguebougou, Mali (N=240)

Double-blind, randomized, phase 1 clinical trial

1. Group 2: Pfs230D1M-EPA/AS01 (n=120)

- **Arm 2c** (n=60), to receive 40 µg Pfs230D1M-EPA/AS01 on D0, D28, D168, and a fourth dose of 40 µg on D476
- **Arm 2d** (n=60), to receive 40 µg Pfs230D1M-EPA/AS01 on D0, D28, then 8 µg Pfs230D1M-EPA/AS01 (*fractional dose*) on D168, and a fourth dose of 40 µg on D476

2. Group 4: Comparators (n=120)

- **Arm 4c** (n=120), to receive ENGERIX-B on D0, D28, and D168 (start study with Arm 2c and 2d), and Menactra[®] on D476.

The multisite study in Mali is designed in a stepwise manner such that each dose of the TBVs is administered in a dose-escalating fashion, and each vaccine (either Pfs25M-EPA/AS01 or Pfs230D1M-EPA/AS01) is administered first as a single vaccination at the target dose before it is administered simultaneously. Additionally, two doses of each vaccine will be administered and assessed for safety as outlined in **Section 12.14.4** and **Appendix A** prior to implementation of the first vaccination in the double blind portion of the study.

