7.6 Prohibited Medications and Procedures

Treatment with any of the following medications/procedures could potentially interfere with vaccine-induced immunity and will not be permitted. Use of any of these during the study may exclude a subject from receiving further doses of the study vaccine. However, the subject will be encouraged to remain in the study for safety evaluations.

- Licensed killed vaccines in the two week period prior to and following each vaccination or licensed live vaccines in the four week period prior to and following each vaccination.
- Receipt of immunoglobulins and/or any blood products up to 6 months prior to the first vaccination and for 30 days after administration of the last dose of vaccine.
- Chronic oral or intravenous administration (≥ 30 days) of immunosuppressive doses of steroids, i.e., prednisone >10 mg per day, immunosuppressants, or other immune-modifying drugs from each day of vaccination to 2 weeks following each vaccination.
- Any investigational drug or investigational vaccine other than the study vaccine during the study period.
- Required surgical removal of the spleen or the development of a hematologic or other disease that would interfere with normal immunity.

Over-the-counter medications, such as acetaminophen or ibuprofen, may be used to help relieve symptoms from vaccination and are not considered prohibited.

Use of antimalarial medications or antibiotics that have antimalarial activity administered during the study period is not exclusionary, but will be documented by clinical staff and will be taken into consideration during data analysis.

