12.3.2 Causality

Causality (likelihood that the event is related to the study agent) will be assessed considering the factors listed under the following categories:

Definitely Related

- reasonable temporal relationship
- follows a known response pattern
- clear evidence to suggest a causal relationship
- there is no alternative etiology

Probably Related

- reasonable temporal relationship
- follows a suspected response pattern (based on similar agents)
- no evidence of a more likely alternative etiology

Possibly Related

- reasonable temporal relationship
- little evidence for a more likely alternative etiology

Unlikely Related

- does not have a reasonable temporal relationship
- OR
- good evidence for a more likely alternative etiology

Not Related

- does not have a temporal relationship
- OR
- definitely due to an alternative etiology

Note: Other factors will also be considered for each causality category when appropriate. Causality assessment is based on available information at the time of the assessment of the AE.

The investigator may revise the causality assessment as additional information becomes available.

The degree of certainty with which an AE can be attributed to administration of the study vaccine will be determined by how well the event can be understood in terms of one or more of the following:

- The event being temporally related with vaccination or reproduced on re-vaccination.
- A reaction of similar nature having previously been observed with this type of vaccine and/or formulation.
- The event having been reported in the literature for similar types of vaccines.
- Whether or not there is another identifiable cause.

All local (injection site) reactions will be considered causally related to vaccination. All malaria cases will be reported as not related to vaccination. Asymptomatic parasitemia (positive blood smears without related malaria clinical symptoms) will not be reported as an AE. Clinical malaria will be reported as an AE.

Reports will further classify AEs as follows:

- Related - all AEs that are assessed as definitely, probably, or possibly related.
- Unrelated - all AEs assessed as unlikely or definitely not related.

When reporting to regulatory authorities and IRBs is needed, AE relationship will be determined as noted above.

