12.13 Unblinding

Intentional, unscheduled unblinding may occur if a subject experiences a SAE that the treating clinician and/or site PI believes warrants unblinding to provide appropriate clinical management of the subject. The request for unblinding may be requested by the site PI or designee, Sponsor, Sponsor Medical Monitor, Independent Medical Monitor, and Data Safety Monitoring Board (DSMB). If non-emergent, all parties should be notified to discuss prior to unblinding taking place. If unblinding is requested, an “Unblinding Report” should be documented per standard operating procedures and submitted to the study statistician for formal unblinding.

If emergency unblinding is required, the PI or designee will contact the study statistician or study pharmacist for unblinding. The Sponsor will be informed within 1 business day that the unblinding was necessary and a submitted “Unblinding Report” will be provided within 2 business days.

Subjects who are unblinded will be encouraged to remain in the study to be followed for safety.

After the time of unblinding, subjects in the experimental vaccine cohort will be offered vaccination with ENGERIX-B, or another FDA-approved Hepatitis B containing vaccine, according to the usual, FDA approved schedule.

Scheduled unblinding for Arms 2c, 2d, 4c will occur on Study Day 336 as already outlined in [Appendix B](#) and [C](#). Scheduled unblinding will be reported to the DSMB at the time of the next meeting.

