14.2 Primary Objective

The primary objective of this study is to assess safety and reactogenicity of Pfs25M-EPA/AS01 and Pfs230D1M-EPA/AS01 in Malian adults.

- The frequency of systemic and local AEs will be summarized.
- A line listing of each clinical and laboratory AE classified as local, solicited, or other will be displayed in tables stratified by vaccine allocation.
- AEs will be summarized by severity and relationship to vaccine
- The proportion of subjects with at least 1 AE will be compared by vaccine schedule and/or dose group, and tests will be performed to assess whether these groups differ with respect to these proportions. To evaluate the difference in AEs between the initial vaccination and the subsequent vaccinations, a Wilcoxon signed rank test will be performed, where the response for each subject is the difference between the numbers of AEs in the 7 days following each vaccination. To compare number and severity of AEs between control and vaccine arms, Wilcoxon-Mann-Whitney test (also known as Wilcoxon rank sum test and the Mann-Whitney U test) tests as well as linear regression may be used.
- SAEs occurring within the study period will be listed by relationship to vaccine.

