3. Record AEs and concomitant medications, if applicable.
4. Obtain approximately 7 mL of blood for malaria blood smear, malaria PCR, SMFA, and anti-Pfs230 antibody ELISA.

Study Day 308 (±21 days; 140 days after Vaccination #3)

1. Perform basic history and focused physical examination, emphasizing examination of any acute complaints.
2. Record vital signs (blood pressure, temperature, and heart rate).
3. Record AEs and concomitant medications, if applicable.
4. Obtain approximately 1 mL of blood for malaria blood smear and malaria PCR.

Study Day 336 (±21 days; 168 days after Vaccination #3)

1. Perform basic history and focused physical examination, emphasizing examination of any acute complaints.

2. Record vital signs (blood pressure, temperature, and heart rate).
3. Record AEs and concomitant medications, if applicable.
4. Obtain approximately 47 mL of blood for malaria blood smear, malaria PCR, SMFA, and anti-Pfs230 antibody ELISA, and cellular assays, *ex vivo* assays, B cell assays and transcriptional analysis.
5. Scheduled unblinding of all subjects
 - a. Offer ENGERIX-B (or other approved Hepatitis B vaccine) to those subjects that received TBV(s) during the study.

Re-enrollment visits

Study Day 462 +/-70 days (294 days after Vaccination #3); Re-screening

1. Explain the study and informed consent document to the subject.
2. Ensure the subject has acknowledged consent by signing or fingerprinting the informed consent document. Ensure that the subject receives a signed copy of the informed consent.
3. Elicit a complete medical history, including menstrual and contraceptive history and/or history of surgical sterility for females, and medication use.
4. Females of childbearing potential must be willing to use reliable contraception from at least 21 days prior to fourth vaccination through three months after the fourth vaccination.
5. Administer a complete physical examination, including vital signs (height, weight, blood pressure, temperature, and heart rate).
6. HIV pre- and post-test counseling as indicated including follow-up contact with subject to report the results and referral for appropriate medical care if indicated.
7. Obtain approximately 16 mL of blood for complete blood count (CBC) with differential and platelet count, ALT, creatinine (Cr), hepatitis B surface antigen, hepatitis C antibody, HIV antibody, malaria blood smear, malaria PCR, SMFA, and anti-Pfs230 antibody ELISA.

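### Only the vaccine arms are offered hepatitis B vaccine from Day 336, and no rule keeps reactions to it out of the booster-phase adverse event comparison with controls

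*Combined protocol and SAP*

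**What the plan says.** **The offer.** For Arms 2c, 2d and 4c, Appendix C places the offer at the Day 336 visit (window ±21 days), together with unblinding: "Offer ENGERIX-B (or other approved Hepatitis B vaccine) to those subjects that received TBV(s) during the study". Section 12.13 repeats that "subjects in the experimental vaccine cohort will be offered vaccination with ENGERIX-B", or another hepatitis B product, "according to the usual, FDA approved schedule". Section 7.2.1 gives that schedule for ENGERIX-B as 0, 1 and 6 months and names TWINRIX as a possible alternative. Under Section 5.1, Arm 4c received ENGERIX-B on Days 0, 28 and 168. It has no later offer.

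**The booster.** Appendix C sets Vaccination #4 at Day 476 ±56, with AEs recorded at each visit to Day 812. The Précis instead places it about one year after Vaccination #3. Section 5.1.2 makes this phase open label.

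**AE rules.** Section 12.3 records solicited events through Day 7 after each vaccination or until resolved; after that it keeps unsolicited AEs, SAEs, unanticipated problems and new chronic illness. Section 12.3.2 adds: "All local (injection site) reactions will be considered causally related to vaccination".

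**Analysis.** Section 5.2.1 makes AE incidence in Arms 2c, 2d and 4c a primary endpoint. Section 14.2 names Wilcoxon-Mann-Whitney (WMW) tests and linear regression as methods that may be used "To compare number and severity of AEs between control and vaccine arms". Section 14.5 plans Fisher's exact test on all AE proportions.

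**Spacing.** Section 7.6 does not permit "Licensed killed vaccines in the two week period prior to and following each vaccination". Exclusion 17 in Section 6.5 covers the two weeks before.

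**The concern.** The booster-phase safety question is a comparison of Arms 2c and 2d with Arm 4c. If accepters in 2c and 2d receive a further, non-study injection during that follow-up and controls do not, reactions to it enter one side only. Nothing in the plan says how such reactions are recorded, attributed or analysed.

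The timing is peculiar to this offer. In the pilot arms the hepatitis B offer comes at the last visit (Day 532), and the Menactra offer to boosted subjects also comes at the last visit (Day 812). Only the main-study hepatitis B offer precedes further safety follow-up. The nominal third-dose days also coincide with twice-weekly feeding visits (Days 504, 507, 511, 514 and 518), each of which records AEs, so reactions would probably be captured. The effect would be to overstate total and related AEs under Pfs230D1M-EPA/AS01.

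**Working it through.** **1. The plan's own dates.** Vaccination #4 minus Vaccination #3: 476 − 168 = 308 days, as Appendix C states. Table 16 agrees: 10 + 336/7 = week 58 (unblinding) and 10 + 476/7 = week 78 (booster).

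**2. Third hepatitis B dose, started on Day 336.** Six months is taken as 168 to 182 days.
- 336 + 168 = Day 504; 336 + 182 = Day 518.
- Against a Day 476 booster: +28 to +42 days, before Day 812.
- Across both windows (start Day 315–357, booster Day 420–532): from (315 + 168) − 532 = −49 to (357 + 182) − 420 = +119 days.
- With the booster at about one year after Vaccination #3 (168 + 364 = Day 532): 14 to 28 days before it.
- If every day of both windows is equally likely and independent (assumption), the dose follows the booster in 74–86% of combinations and lies within 14 days of it in 21–25%.
- Dose 2 (about Day 343–388) always precedes the earliest booster, Day 420.

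**3. AEs added per vaccine-arm subject** = uptake × reaction rate. Uptake is not stated; 50–100% is assumed. Section 15.4.2.2 says only that injection-site pain and fatigue each occur in at least 10% after ENGERIX-B. Table 2B gives 28–48% local reactions per dose for Euvax B, a different product.
- 10% rate: 0.5 × 0.10 = 0.05 to 1 × 0.10 = 0.10.
- 30% rate: 0.15 to 0.30.
- 48% rate at full uptake: 0.48.

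**4. WMW type I error, no true difference, 108 v 108** (Section 14.5 assumes 10% dropout from 120; the same is applied to controls). Counts are negative binomial with dispersion 4 or 20 (assumed). A mean of 4.0 comes from Table 2B, 161/40 after dose 4. That study followed subjects for at least 6 months; here follow-up is 336 days, so at a constant rate the mean is about 4.0 × 336/168 = 8.

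| Added AEs | Mean 4 | Mean 8 |
|---|---|---|
| 0 | 5–6% | 5% |
| 0.05–0.10 | 5–7% | 5–6% |
| 0.15 | 6–8% | 6% |
| 0.30 | 13–18% | 7–11% |
| 0.48 | 26–36% | 10–19% |

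Simulation error near 8% with 3,000 runs is about 1.96 × √(0.08 × 0.92/3000) = 1 percentage point.

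**5. Fisher's test on a narrow category such as related AEs** (background proportion p assumed). The vaccine-arm proportion becomes p + (1 − p) × uptake × rate. With p = 0.20:
- 10% rate, 50% uptake: 0.20 + 0.80 × 0.05 = 0.24, falsely significant in 8% of trials (3.3% with nothing added).
- 30% rate, 50% uptake: 0.20 + 0.80 × 0.15 = 0.32, 46%.
- 48% rate, full uptake: 0.58, nearly 100%.

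With p = 0.40 the range is 5–99%. For any AE at all, Table 2B shows 100% of subjects in both arms after dose 4, so that proportion cannot move.

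**The case against.** Several stronger readings are tempting, and the documents do not support them.

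- *Every reaction to the offered vaccine is automatically charged to the study vaccine.* The rule covers local reactions only; other events are judged by the investigator against the study agent. Section 12.3.2 opens by defining causality in relation to the study agent, so vaccination in the local-reaction sentence may well mean study vaccination. The wording leaves this open, which is a reason to clarify it.
- *Booster reactogenicity is contaminated.* If the two-week rule is followed, the offered dose stays out of the 7 days after the booster. Solicited reactogenicity and the 7-day signed-rank comparison are protected. Later unsolicited, total and related counts are exposed.
- *The third dose will fall after the booster.* It is an offer, with no stated uptake, date or fixed product, and the windows are wide. A booster near Day 532 would come after the dose.
- *The offer contradicts Section 7.6.* It does not in itself, since the spacing rules apply whatever is offered. A Day 504 dose conflicts only with boosters on Days 490–518. What is missing is any passage coordinating the two.
- *A type I error near one in three is to be expected.* That needs full uptake, the highest reaction rate of another product, and a mean of 4 AEs.

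It is also fair that Section 14.1 calls the study exploratory, that WMW is optional, and that the distortion overstates harm and so would not conceal a safety signal. These points lower the severity. They do not supply the missing rule.

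**Conclusion.** The concern holds in limited form. The one-sided offer, the nominal overlap with booster follow-up and the absence of any rule separating these reactions are all in the documents. Followed literally, the causality and comparison rules would add them to total and related AEs in Arms 2c and 2d only.

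The size is not established. It rests on assumed uptake, reaction rates borrowed from a different hepatitis B product, and assumed AE counts and dispersion. The WMW type I error is about 5–9% for 0.05–0.15 added AEs per subject (simulation error included). It reaches about 35% only at 0.48 added with a mean of 4, and is smaller with a higher AE background. Fisher's test on related AEs could be more sensitive, but its range is too wide to serve as an estimate.

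A reader might infer that the booster's safety comparison is invalid. The documents do not support that: the 7-day data stand if Section 7.6 is kept, and the rest can be repaired in the analysis. This is a cheap improvement.

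**What to change.** 1. In Section 12.3.2, limit the automatic causality rule to reactions at the site of a study injection.
2. In Section 14.2, flag the dates of offered hepatitis B doses from the concomitant-medication record, which is reviewed at every visit. Tabulate separately the local reactions at that injection site and the AEs attributed to that vaccine. Report the booster-phase between-arm AE comparisons with and without them.
3. Reconcile Section 12.13 and the Day 336 entry in Appendix C with Section 7.6, exclusion 17 and the Day 476 ±56 window. How the doses are timed is for the sponsor and investigators to decide.

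Do not simply drop all AEs within 7 days of an offered dose. That removes AE time from the vaccine arms only, about 4.0 × 7/168 = 0.17 AEs per subject at full uptake, similar to the 0.15 it might correct. In simulation it gave roughly 5–9% rejection, with the distortion now favouring the vaccine.

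Cost: one flag, one clarifying phrase and one more set of AE tables. No treatment changes.

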Appendix D: Toxicity Table**Local Reactogenicity Grading¹**

Local Reaction to Injectable Product	Mild (Grade 1)	Moderate (Grade 2)	Severe (Grade 3)	Potentially Life Threatening (Grade 4)
Pain	Does not interfere with activity	Repeated use of non-narcotic pain reliever > 24 hours or interferes with activity	Any use of narcotic pain reliever or prevents daily activity	Emergency room (ER) visit or hospitalization
Tenderness	Mild discomfort to touch	Discomfort with movement	Significant discomfort at rest	ER visit or hospitalization
Erythema/Redness²	2.5 – 5 cm	5.1 – 10 cm	> 10 cm	Necrosis or exfoliative dermatitis
Induration/Swelling³	2.5 – 5 cm and does not interfere with activity	5.1 – 10 cm or interferes with activity	> 10 cm or prevents daily activity	Necrosis
Pruritus at Site	Does not interfere with activity	Repeated use of medication > 24 hours or interferes with activity	Prevents daily activity	ER visit or hospitalization
Limitation of Arm Movement	Does not interfere with activity	Repeated use of medication > 24 hours or interferes with activity	Prevents daily activity	ER visit or hospitalization

¹ The definitions provided in the table are taken from the FDA Guidance for Industry “Toxicity Grading Scale for Healthy Adults and Adolescent Volunteers Enrolled in Preventive Vaccine Clinical Trials” dated September 2007.

² In addition to grading the measured local reaction at the greatest single diameter, the measurement should be recorded as a continuous variable.

³ Induration/Swelling should be evaluated and graded using the functional scale as well as the actual measurement.

Vital Sign AE Grading¹

Vital Signs²	Mild (Grade 1)	Moderate (Grade 2)	Severe (Grade 3)	Potentially Life Threatening (Grade 4)
Fever³ (°C) (°F)	38.0 – 38.4 100.4 – 101.1	38.5 – 38.9 101.2 – 102.0	39.0 – 40 102.1 – 104	> 40 > 104
Tachycardia - beats per minute	101 – 115	116 – 130	> 130	ER visit or hospitalization for arrhythmia
Bradycardia - beats per Minute⁴	50 – 54	45 – 49	< 45	ER visit or hospitalization for arrhythmia
Hypertension (systolic) - mm Hg	141 – 150	151 – 155	> 155	ER visit or hospitalization for malignant hypertension
Hypertension (diastolic) - mm Hg	91 – 95	96 – 100	> 100	ER visit or hospitalization for malignant hypertension
Hypotension (systolic) – mm Hg	85 – 89	80 – 84	< 80	ER visit or hospitalization for hypotensive shock

¹ The definitions provided in the table are taken from the FDA Guidance for Industry “Toxicity Grading Scale for Healthy Adults and Adolescent Volunteers Enrolled in Preventive Vaccine Clinical Trials” dated September 2007.

² Subject should be at rest for all vital sign measurements.

² Oral temperature; no recent hot or cold beverages or smoking.

³ When resting heart rate is between 60 – 100 beats per minute. Use clinical judgment when characterizing bradycardia among some healthy subject populations, for example, conditioned athletes.

Systemic AE Grading¹

Systemic AEs	Mild (Grade 1)	Moderate (Grade 2)	Severe (Grade 3)	Potentially Life Threatening (Grade 4)
Diarrhea	2 – 3 loose stools or < 400 gms/24 hours	4 – 5 stools or 400 – 800 gms/24 hours	6 or more watery stools or > 800gms/24 hours or requires outpatient IV hydration	ER visit or hospitalization
Headache	No interference with activity	Repeated use of non-narcotic pain reliever > 24 hours or some interference with activity	Significant; any use of narcotic pain reliever or prevents daily activity	ER visit or hospitalization
Malaise	No interference with activity	Some interference with activity	Significant; prevents daily activity	ER visit or hospitalization
Myalgia	No interference with activity	Some interference with activity	Significant; prevents daily activity	ER visit or hospitalization
Arthralgia	No interference with activity	Some interference with activity	Significant; prevents daily activity	ER visit or hospitalization
Nausea/ Vomiting	No interference with activity or 1 – 2 episodes/24 hours	Some interference with activity or > 2 episodes/24 hours	Prevents daily activity, requires outpatient IV hydration	ER visit or hospitalization for hypotensive shock
Urticaria	No interference with activity	Requiring PO or topical treatment > 24 hours or IV medications or steroids for ≤24 hours	Requiring IV medication or steroids for >24 hours	ER visit or hospitalization

¹ The definitions provided in the table are taken from the FDA Guidance for Industry “Toxicity Grading Scale for Healthy Adults and Adolescent Volunteers Enrolled in Preventive Vaccine Clinical Trials” dated September 2007.

Mali Laboratory AE Grading

Hematology/Chemistry

Hematology and Biochemistry values ^{1,2}	Mild (Grade 1)	Moderate (Grade 2)	Severe (Grade 3)	Potentially Life Threatening (Grade 4)
Hemoglobin (Male) - gm/dL	9.5 – 10.5	8.0 – 9.4	6.5 – 7.9	< 6.5 and / or requiring transfusion
Hemoglobin (Female) gm/dL	8.0 – 9.0	7.0 – 7.9	6.0 – 6.9	< 6 and /or requiring transfusion
WBC Increase – 10 ³ /μL	11.5 – 15.0	15.1 – 20.0	20.1 – 25.0	> 25.0
WBC Decrease - 10 ³ /μL	2.5 – 3.3	1.5 – 2.4	1.0 – 1.4	< 1.0
Neutrophil/Granulocyte Decrease ³ - 10 ³ /μL	0.80 – 1.00	0.50 – 0.79	< 0.50	< 0.50 with fever
Platelets Decreased – 10 ³ /μL	100 – 115	70 – 99	25 – 69	< 25
Creatinine (Male) μmol/L	132.60 – 159.11	159.12 – 185.63	185.64 – 221.00	> 221.00 and requires dialysis
Creatinine (Female) μmol/L	97.42 – 116.94	116.95 – 136.44	136.45 – 162.43	> 162.43 and requires dialysis
Liver Function Tests – ALT U/L	46.0 – 106.5	106.6 – 209.0	209.1 – 410.0	> 410.0

¹ The laboratory values provided in the table are taken from the FDA Guidance for Industry “Toxicity Grading Scale for Healthy Adults and Adolescent Volunteers Enrolled in Preventive Vaccine Clinical Trials” dated September 2007. The laboratory values provided in the referenced tables serve as guidelines and have been adapted for institutional normal parameters (see below). Institutional normal reference ranges should be provided to demonstrate that they are appropriate.

² The clinical signs or symptoms associated with laboratory abnormalities might result in characterization of the laboratory abnormalities as Potentially Life Threatening (Grade 4). For example, a low sodium value that falls within a grade 3 parameter should be recorded as a grade 4 hyponatremia event if the subject had a new seizure associated with the low sodium value.

³ Note, neutropenias are graded and followed, but based on previous experience in African populations, should be interpreted with caution since lower values are more frequently observed in people of African descent ^{46,47}.

Mali Adult: Institutional Normal Parameters**Chemistry**

Serum¹	Reference Range
Creatinine (Female) - $\mu\text{mol/L}$	< 72
Creatinine (Male) - $\mu\text{mol/L}$	48 – 98
ALT – U/L	< 41

¹The laboratory values provided in the table are based on Bancoumana, Malian adults (age 18-45 years old)

Hematology

Hematology¹	Reference Range
Hemoglobin (Female) - gm/dL	9.1 – 13.8
Hemoglobin (Male) - gm/dL	10.8 – 15.8
WBC – $10^3/\mu\text{L}$	3.6 – 9.0
Absolute Neutrophil/Granulocyte Count - $10^3/\mu\text{L}$	1.3 – 4.4
Absolute Lymphocyte Count - $10^3/\mu\text{L}$	1.3 – 4.4
Platelet Count (Female)- $10^3/\mu\text{L}$	144 – 413
Platelet Count (Male)- $10^3/\mu\text{L}$	114 – 335

¹The laboratory values provided in the table are based on Bancoumana, Malian adults (age 18-45 years old)

Urine Dip/Urinalysis

Urine¹	Reference Ranges
Protein	None or Trace
Blood (microscopic) – red blood cells per high power field (RBC/HPF)	None or Trace < 5

¹The laboratory values provided in the table are based on Bancoumana, Malian adults (age 18-45 years old)

